6.13.6. Electrocardiograms

ECG measurements will be analyzed using continuous data (change from baseline) and categorical data (proportion of treatment-emergent abnormalities).

The analysis will be done for the following ECG measurements: heart rate, PR, QT, QTc, and RR intervals and QRS duration. All analyses of QTc will be carried out using the Fridericia correction (QTcF) method. These summaries will include data from each visit ECG measures are performed. In the Placebo-Controlled period, change from baseline to each post-baseline visit at which ECG measurements are taken will be assessed using an MMRM model. The model for the fixed effects will include terms for the following independent effects: baseline ECG score, treatment, visit, treatment-by-visit interaction, and age at baseline. This analysis will be done separately for each ECG parameter. These change from baseline will be summarized in the Delayed-Start period.

In the Placebo-Controlled period, incidence of treatment-emergent abnormal ECGs will be assessed by comparisons at (1) anytime and (2) each post-baseline visit between treatment groups with Fisher's Exact test. For analyses of treatment-emergent abnormal ECGs, baseline will be considered as all visits before the initiation of drug dose. For the Delayed-Start period, these incidences will be summarized.

Abnormal ECG criteria and criteria for abnormal QTcF prolongation are presented in Appendix 6. A second summary of QTc intervals will compare incidence of treatment-emergent increases at any time in four different groups: < 30msec, 30 <= and < 60 msec, > 60 msec, and > 75 msec. This second summary will correct the QT intervals using Fridericia correction (QTcF) and using a large clinical trial population based correction factor (QTcLCTPB).

Treatment-emergent high ECG parameters (heart rate, PR interval, QRS duration, QT and QTcF intervals) are the values which are low or normal at all baseline visits and fall into the high abnormal categories post-baseline. Similarly, treatment-emergent low ECG parameters (Heart Rate, PR interval, QRS duration) are the values which are high or normal at all baseline visits and fall into the low abnormal categories above.

In the Placebo-Controlled period, treatment differences in the proportion of subjects who have normal baselines with a change to abnormal high or abnormal low values at any post-baseline visits will be summarized. In the Delayed-Start period, these proportions will be summarized.

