### 9.4.9.1. Adverse Events of Special Interest

Adverse events of special interest will include:

- Adverse eye effects including retina (Section 9.4.7)
- Adverse skin effects including rash (Section 9.4.9.3) and hypopigmentation (Section 9.4.8)
- Peripheral nervous system, central nervous system and muscle effects
- Liver toxicity (Section 9.4.9 and Section 8.1.1)
- Cardiovascular (CV)-type events (including, but not limited to, orthostatic hypotension and QT prolongation) (Section 9.4.9.2)

The topics listed above, as well as new topics which may be subsequently determined by the Sponsor, will be subject to enhanced surveillance activities. Additionally, the topics above will be analyzed for presentation in the Clinical Study Report in accordance with the Statistical Analysis Plan (SAP).

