Appendix 5. Potentially Clinically Significant ECGs

Parameter	Unit	Low PCS Criteria	High PCS Criteria
QRS Interval	msec	NA	≥120
PR Interval	msec	<100	≥220
Heart Rate	bpm	<45	≥120
QTcF	msec	<320	>500
QTcF interval: change from baseline	>60 msec at any time after randomization		

Abbreviation: PCS = potentially clinically significant.

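### The QTc increase groups in SAP 6.13.6 leave an increase of exactly 60 msec unassigned and do not say whether the group above 75 msec is a subset of the group above 60 msec.

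*SAP*

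**What the plan says.** SAP section 6.13.6 (Electrocardiograms) describes the summary and its groups as follows: "A second summary of QTc intervals will compare incidence of treatment-emergent increases at any time in four different groups", namely "< 30msec, 30 <= and < 60 msec, > 60 msec, and > 75 msec". It applies them under two corrections: "This second summary will correct the QT intervals using Fridericia correction (QTcF) and using a large clinical trial population based correction factor (QTcLCTPB").

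SAP Appendix 5 has one separate criterion for change in QTcF: ">60 msec at any time after randomization". It has none for QTcLCTPB. (Section 6.13.6 points to an Appendix 6 for the ECG criteria, but they stand in Appendix 5, the last one listed.)

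Protocol section 9.4.9.1 includes "orthostatic hypotension and QT prolongation" among the cardiovascular events of special interest.

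**The concern.** A table of graded increases is normally read in one of two ways. Either the rows are exclusive bands that add up to the number of evaluable patients, or they are rising thresholds, each counting everyone above it. The list in section 6.13.6 mixes the two. The first two rows are bands. The last two are open-ended thresholds, one inside the other. Between the second and third rows a single value is left out.

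Two things follow if the text is programmed literally. A patient whose largest increase is exactly 60 msec is counted in the denominator but appears in no row. And a reader cannot tell whether the rows should sum to the denominator, because anyone above 75 msec is counted twice unless the programmer decides otherwise. The protocol treats QT prolongation as a topic for close watch, so the rule should be settled in the SAP and not left to whoever programs the table.

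**Working it through.** The plan gives no figure to reproduce here. The check is one of logic: take the four groups as written, assign each possible change to them, and count how many groups it meets.

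**Inputs.** Groups from SAP 6.13.6, with x the change in msec: (1) x < 30; (2) 30 ≤ x < 60; (3) x > 60; (4) x > 75. From SAP Appendix 5: QTcF change criterion x > 60.

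**Step 1: groups as written.** Every whole-millisecond value from -100 to +150 was assigned, with a few fractional values near the boundary.

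| Change (msec) | Groups met as written | Count |
|---|---|---|
| 29 | (1) | 1 |
| 30 | (2) | 1 |
| 59 | (2) | 1 |
| 59.9 | (2) | 1 |
| **60** | **none** | **0** |
| 60.1 | (3) | 1 |
| 61 | (3) | 1 |
| 75 | (3) | 1 |
| **76** | **(3) and (4)** | **2** |

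Across the whole range, 60 is the only whole value that meets no group. Every value from 76 to 150 meets two. All the others meet exactly one.

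**Step 2: can another passage place the value 60?** Appendix 5 says only that 60 does not meet the QTcF change criterion, because that criterion is strict. It does not assign 60 to a row of this table, and it does not cover QTcLCTPB. No other section of the SAP or protocol gives a rule.

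**Step 3: does the nested reading remove the gap?** No. If the last two rows are cumulative, the double count above 75 is explained, but 60 still fails both x < 60 and x > 60.

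**Step 4: corrected groups.** With x < 30; 30 ≤ x ≤ 60; 60 < x ≤ 75; x > 75, every value from -100 to +150 meets exactly one group. The last two groups together equal x > 60, so for QTcF their total matches the Appendix 5 cut.

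**The case against.** The strongest reply concerns the overlap. The summary is about incidence, and incidence above rising thresholds is often shown cumulatively. The same SAP does this in section 6.13.4, where ALT at or above 5 and 10 times the upper limit of normal are listed side by side, so a patient at 10 times meets both. On that reading the last two rows are nested by design and nobody is wrongly counted twice. This largely stands. A reader might infer that the overlap is an error on a par with the gap, but the documents do not support that. They support only that the wording, which calls these different groups, does not say the rows are cumulative, so a label is needed.

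A second reply is that little is lost. A patient at exactly 60 msec on QTcF does not meet the strict Appendix 5 criterion in any case, and still contributes to the repeated-measures analysis of QTcF change. The counts above 60 and above 75 are right as they are; only the middle row can be short. This also stands. A reader might infer that patients at a key safety cut-off disappear from the safety reporting. They do not: they are missing from one table. For QTcLCTPB, though, this summary is the only use that section 6.13.6 describes.

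A third reply is that the events of special interest are analysed through MedDRA clusters (SAP section 6.13.3, including the torsades/QT prolongation query), which do not use these ECG groups. That is correct. The special-interest listing shows why QT matters in this trial, but that analysis is unaffected.

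None of these replies places the value 60.

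**Conclusion.** The gap at exactly 60 msec is a stated rule that is wrong as written, under either reading of the upper rows and under both corrections. The relation between the two upper groups is unclear but not shown to be wrong.

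The effect is small. It touches one descriptive safety table. SAP section 6.1 already says that no test will be interpreted as statistically significant. The efficacy analyses, the Appendix 5 criterion above 60 msec and the MedDRA clusters do not change.

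No patient count can be attached. A reader might be tempted to multiply the planned 1899 patients by some share of ties at 60. The documents give no distribution of QTc change and do not say that corrected values are held as whole milliseconds. Also, 1899 is the planned randomized total, whereas protocol section 10.3.4 restricts ECG abnormality comparisons to patients with both a baseline and a postbaseline value. The number affected may be zero. The finding rests only on the inequalities as printed.

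**What to change.** In SAP section 6.13.6, for both QTcF and QTcLCTPB, use one of the following:

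- **Exclusive bands:** <30, ≥30 to ≤60, >60 to ≤75, and >75 msec. The rows then sum to the number of evaluable patients.
- **Bands with a subset row:** <30, ≥30 to ≤60, and >60 msec, followed by >75 msec labelled as part of the >60 row. The first three rows sum to the denominator.

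Both put exactly 60 in the middle band, which agrees with the strict cut in Appendix 5. Starting the upper band at ≥60 would also close the gap, but a patient at 60 on QTcF would then fall in the upper band here while not meeting the Appendix 5 criterion. State the rounding applied to corrected QT values before grouping, so that ties at the boundary are handled in one way.

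The cost is one line in the SAP and the matching line in the table program and row labels. No data collection or other analysis changes.

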6.13.7. Analyses of MRI Data

To evaluate any changes in MRI data following treatment, Pearson's chi-square tests will be used to compare frequencies of responses in the MRI parameters in the Placebo-Controlled period. In the Delayed-Start period, these frequencies will be summarized.

Frequencies and percentages of the following amyloid-related imaging abnormality – edema (ARIA-E, also known as vasogenic edema) and ARIA – hemorrhage (ARIA-H, also known as microhemorrhage) parameters will be summarized:

- ARIA-E:
- o Severity (questionable, mild, moderate, severe, or no presence)
- o Status compared to the previous MRI(s) (questionable, unchanged, increased, decreased, no longer present)
- ARIA-H:
- o Number of ARIA-H (1, 2 to 5, 6 to 10, >10, or no presence),
- o Baseline to endpoint changes (increase in size of pre-existing ARIA-H, increase in number of ARIA-H, no change, partial resolution, or complete resolution)

To evaluate white matter changes over time, a shift table will be created from the following categories:

- 0 = No lesions
- 1 = Focal lesions
- 2 = Beginning confluence of lesions
- 3 = Diffuse involvement of entire region

A listing of MRI data will also be presented by subject and visit across the Placebo-Controlled and Delayed-Start periods.

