- [25] Screening magnetic resonance imaging (MRI) shows evidence of >5 microhemorrhages; prior macrohemorrhage (>1 cm³); ≥4 infarcts, evidence of cerebral contusion, encephalomalacia, space-occupying lesion with mass-effect and edema

Note: Cortical superficial siderosis is not an exclusion.

- [26] Uncontrolled hypertension, that is, supine systolic blood pressure >165 mmHg or diastolic blood pressure >95 mmHg. If an initial blood pressure reading is higher than this, an additional attempt (at this visit or on another day) could be used before excluding a patient for uncontrolled hypertension.
- [27] Known positive serologic findings for human immunodeficiency virus (HIV) antibodies. Local laws and regulations may apply to whether testing is required.
- [28] Patients with past history (suspected or confirmed) of Hepatitis B should have HBsAg testing at screening and are excluded if HBsAg is positive.
  - Patients with past history (suspected or confirmed) of Hepatitis C (resolved >6 months prior to enrollment) should have hepatitis C virus (HCV) ribonucleic acid (RNA) polymerase chain reaction (PCR) testing at screening and are excluded if HCV RNA PCR is positive.
  - Patients in high-prevalence regions may be required to have screening serology.
- [29] Any clinically important abnormality at screening, as determined by investigator, in physical or neurological examination, vital sign, ECG, or clinical laboratory test results that could be detrimental to the patient or could compromise the study
- [30] Calculated creatinine clearance <30 mL/min (Cockcroft-Gault formula; Cockcroft and Gault 1976) at screening
- [31] Alanine aminotransferase (ALT)  $\geq$ 2x the upper limit of normal (ULN) of the performing laboratory, aspartate aminotransferase (AST)  $\geq$ 2x ULN, total bilirubin  $\geq$ 1.5x ULN, or alkaline phosphatase (ALP)  $\geq$ 1.5x ULN at screening

NOTE: Patients with total bilirubin  $\ge$ 1.5 x ULN are not excluded if they meet all of the following criteria for Gilbert syndrome:

- 1. Bilirubin is predominantly indirect (unconjugated) at screening (direct bilirubin within normal limits)
- 2. Absence of liver disease
- 3. ALT, AST, and ALP ≤1x ULN at screening
- 4. Hemoglobin not significantly decreased at screening

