### 9.4.9.4. Vasogenic Edema

If a patient develops symptoms suggestive of vasogenic edema, such as headache, confusion, gait disturbance, or visual disturbance, these should be recorded as AEs and an MRI should be obtained. Study treatment should be discontinued if clinically significant symptomatic vasogenic edema, clinically significant symptomatic superficial siderosis, or clinically significant symptomatic incident microhemorrhage is seen. Following the study treatment discontinuation, the MRI scan should be repeated within 4 weeks to evaluate the status of the finding and then performed every 4 to 6 weeks (or as clinically indicated) until the finding resolves or stabilizes. Treatment with high-dose dexamethasone is to be considered, should symptoms be severe.

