#### 10.3.4. Safety Analyses

Safety will be assessed by summarizing and analyzing AEs, laboratory analytes, vital signs, MRI scans, skin and eye examinations, and ECGs during the treatment period.

Safety analyses for the Placebo-Controlled period will include comparisons between LY3314814 dose groups and placebo. All hypotheses will be tested at a 2-sided 0.05 significance level. No adjustments for multiple comparisons will be made.

Safety analyses for the Delayed-Start period will incorporate a "contextualizing cohort" developed through modeling the plausible progression of disease for a placebo treated cohort. Further details on this modeling approach and the analysis methods will be outlined in the SAP.

For analysis comparing proportion of treatment-emergent abnormalities between treatment groups for laboratory analytes, vital signs, weight, MRI scans, skin and eye examinations, and ECGs, only patients who have both a baseline observation and a postbaseline observation will be included in the analysis for each analyte or parameter, respectively.

Suicide-related thoughts and behaviors, based on the C-SSRS, will be listed by patient and visit. Only patients that show suicidal ideation/behavior will be displayed (that is, if a patient's answers are all "no" for the C-SSRS, then that patient will not be displayed). However, if a patient reported any ideation or behavior at any time point, then all their ideation and behavior will be displayed, even if not positive.

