6.1.1. Placebo-Controlled Period

Data summaries will include a total column and columns describing the treatments received only in the Placebo-Controlled period: 20mg, 50mg, or PLA. When change from baseline is assessed, subjects will be included in the analysis only if both a baseline and a post-baseline measurement are available. Unless otherwise defined, a baseline measurement is the last non-missing observation collected during Visits 1 and 2. End point is the last non-missing post-baseline measurement prior to the Delayed-Start period. For analyses using last observation carried forward (LOCF), the last non-missing post-baseline measurement (scheduled or unscheduled) will be used to calculate change from baseline. With the early termination of this study, all results are considered to be suggestive or hypothesis-generating rather than the originally planned confirmatory interpretation of the test or comparison.

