6.1.2. Delayed-Start Period

Unless otherwise defined, a baseline measurement is the last non-missing observation collected prior to the Delayed Start period. No between treatment p-values will be reported because (1) all patients received active treatment in the Delayed Start period, and (2) previous treatments in the Placebo-Controlled period were randomized at baseline and do not guarantee patients entering the Delayed Start period are without selection bias. Data summaries will include a total column and columns describing the treatments received across both study periods: 20mg, 50mg, PL/20 and PL/50.

When change from baseline is assessed, subjects will be included in the analysis only if both a baseline and a post-baseline measurement are available. Endpoint is the last non-missing post-baseline measurement. For analyses using last observation carried forward (LOCF), the last non-missing post-baseline measurement (scheduled or unscheduled) will be used to calculate change from baseline.

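### The SAP's MRI safety section defines no treatment-emergent ARIA outcome over all post-baseline scans, so pre-existing ARIA-H is counted with new ARIA-H and a transient new ARIA-H can read as unchanged

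*SAP*

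**What the plan says.** Protocol 10.3.4 (Safety Analyses) presupposes a treatment-emergent MRI comparison: "For analysis comparing proportion of treatment-emergent abnormalities between treatment groups for laboratory analytes, vital signs, weight, MRI scans" is the start of a sentence that restricts the denominator to patients with both a baseline and a postbaseline observation.

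SAP 6.13.7 (Analyses of MRI Data) tabulates four ARIA variables and compares them by Pearson's chi-square test in the Placebo-Controlled period:

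- ARIA-E severity.
- ARIA-E status: "Status compared to the previous MRI(s) (questionable, unchanged, increased, decreased, no longer present".
- ARIA-H number: "Number of ARIA-H (1, 2 to 5, 6 to 10, >10, or no presence".
- ARIA-H change: "Baseline to endpoint changes (increase in size of pre-existing ARIA-H, increase in number of ARIA-H, no change, partial resolution, or complete resolution".

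A listing of MRI data by subject and visit is also planned.

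Other sections bear on how these are read. SAP 6.1.1 states "End point is the last non-missing post-baseline measurement prior to the Delayed-Start period". For the Delayed-Start period, SAP 6.1.2 states that "a baseline measurement is the last non-missing observation collected prior to the Delayed Start period". Exclusion criterion [25] applies when "Screening magnetic resonance imaging (MRI) shows evidence of >5 microhemorrhages", so a patient may enter with up to 5. Protocol Tables 2.1 to 2.3 schedule MRI at screening, at Week 78 or early discontinuation, and at Week 156 or early discontinuation. Protocol 9.4.6 adds scans when clinically indicated. After treatment is stopped for a clinically significant symptomatic finding, Protocol 9.4.9.4 says that "the MRI scan should be repeated within 4 weeks to evaluate the status of the finding and then performed every 4 to 6 weeks" until the finding resolves or stabilizes.

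**The concern.** Detecting ARIA is the stated purpose of the safety MRI (Protocol 9.4.6). The natural safety question is how many patients in each arm had ARIA after dosing that was not there before, on any scan. None of the four variables answers it directly. One counts lesions whatever their origin, one looks only at the last scan, one has no category for a first appearance, and one does not say which scan it uses.

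The gap stands out against the neighbouring sections. Laboratory values, vital signs and ECGs (SAP 6.13.4 to 6.13.6) are assessed for treatment-emergent abnormality at any time and by visit. The skin section (6.13.8.2) takes the maximum during treatment, and the eye section (6.13.8.3) the worst assessment. MRI has no equivalent rule.

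At stake are a between-arm ARIA-H table diluted by lesions that predate dosing, and the loss from that table of new findings that later cleared. The second problem falls on patients who had more than one post-baseline scan, and those extra scans arise largely from symptoms or follow-up of a finding.

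**Working it through.** The plan states no ARIA rate, power or threshold, so there is no figure to reproduce. The check is to score possible scan sequences with the categories in SAP 6.13.7 and the endpoint rule in 6.1.1.

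1. **ARIA-H: none at screening, a lesion on an unscheduled scan, none on the last scan.** Change reads as no change. The new finding is missed.
2. **ARIA-H: none at screening, a lesion at Week 78, no other post-baseline scan.** Change reads as an increase in number. The new finding is counted.
3. **ARIA-H: two lesions at screening, five at Week 78.** The number stays in the band 2 to 5, but the change item records an increase. The new lesions are counted, though only in the change table.
4. **ARIA-H: two lesions at screening, two at Week 78.** The number table places the patient in the band 2 to 5 although nothing is new. Prevalent and new lesions are mixed.
5. **ARIA-E: absent, present on an unscheduled scan, absent again.** On the third scan, status reads as no longer present, so the episode can be inferred. On the second scan, the list has no category for a first appearance. If severity were taken from the last scan it would read as no presence; the SAP does not say whether it is last, worst or by visit.

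Sequences 1 and 5 need at least two post-baseline scans in the period. Table 2.2 plans one, so both depend on an unscheduled or follow-up scan. The early-discontinuation MRI is done only if at least 24 weeks have passed since the previous one, so for some patients the symptom-driven scan is itself the last scan and nothing is masked.

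**Dilution in the number table, as an illustration only.** Let b be the proportion with ARIA-H at screening and i the proportion with a new lesion. If the two are independent and lesions persist:

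- proportion with any ARIA-H = b + (1 − b) × i
- difference between arms = (1 − b) × (i₁ − i₀)

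All rates below are assumptions.

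- New lesions 2% v 5% (difference 3.0 points):
  - b = 10%: 0.10 + 0.90 × 0.02 = 11.8% v 0.10 + 0.90 × 0.05 = 14.5% (2.7 points)
  - b = 20%: 21.6% v 24.0% (2.4 points)
  - b = 30%: 31.4% v 33.5% (2.1 points)
- New lesions 5% v 10% (difference 5.0 points):
  - b = 10%: 14.5% v 19.0% (4.5 points)
  - b = 20%: 24.0% v 28.0% (4.0 points)
  - b = 30%: 33.5% v 37.0% (3.5 points)

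The difference shrinks by the factor (1 − b), on top of a much higher background rate. With b = 0 the two counts coincide. This describes the number table alone, not the change table beside it.

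**The case against.** Three stronger readings are tempting, and the documents do not support them.

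- **The plan has no count of new ARIA at all.** The increase-in-number category counts net new ARIA-H at the last scan and is compared between arms. For a patient with only the scheduled post-baseline scan, that is the quantity wanted.
- **Every change measure runs from baseline to the last scan.** That is true of ARIA-H only. ARIA-E status is judged against the previous MRI(s), so ARIA-E that cleared shows as no longer present.
- **The test loses much of its power.** Setting any ARIA-H present against new ARIA-H leaves out the planned change table and rests wholly on assumed rates. SAP 6.1 also says that, after the futility stop, no test will be interpreted as statistically significant.

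The best defence is that important cases surface elsewhere. Symptoms suggestive of vasogenic edema are to be recorded as AEs (Protocol 9.4.9.4). Clinically significant MRI findings that lead to a diagnosis are reported as pre-existing conditions or AEs (Protocol 9.4.6). SAP 6.13.2 compares treatment-emergent AEs and AEs leading to treatment discontinuation between arms. The serial rescanning follows treatment discontinuation for a clinically significant symptomatic finding, and it stops at resolution or stabilization, so the last scan need not be clear. Protocol 9.4.6 also says that no association of ARIA-E with this drug is known, and Protocol 10.3.1 lets the SAP change methods that are not principal features.

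Much of this stands, and it limits how many patients are affected. It does not remove the gap. A listing is not a comparison between arms. The AE route covers MRI findings only when they are clinically significant and yield a diagnosis. The adverse-event clusters in Table AZET.SAP.2 include none named for ARIA. The SAP gives no reason for dropping the treatment-emergent comparison that Protocol 10.3.4 presupposes.

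**Conclusion.** The point holds in a limited form. SAP 6.13.7 does not carry through the treatment-emergent MRI comparison that Protocol 10.3.4 lists. Three consequences follow from the text alone:

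- the ARIA-H number table counts lesions allowed at entry as responses;
- the stated rules score a transient new ARIA-H as no change;
- ARIA-E has no category for a new finding, and nothing says which scan supplies severity or number when there are several.

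The masking reaches only patients with unscheduled or follow-up scans, and some of their findings will also appear in AE tables. How many patients that is cannot be derived, and no power loss can be stated. The illustrative dilution depends on assumed screening prevalence and new-lesion rates. Because results are now treated as hypothesis-generating, the value of the change lies in a readable, complete count of new ARIA by arm. It is a worthwhile, cheap improvement, not a flaw that invalidates the MRI analysis.

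**What to change.** In SAP 6.13.7 add two yes/no outcomes, summarised by arm and compared in the Placebo-Controlled period. Use every scheduled or unscheduled post-baseline scan in the period, with the pre-treatment screening scan named as the reference:

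- **Treatment-emergent ARIA-E:** absent at screening and present later, or more severe than at screening.
- **Treatment-emergent ARIA-H:** more or larger lesions than at screening.

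Tabulate ARIA-E severity and ARIA-H number at the worst post-baseline scan. The denominator is patients with a screening MRI and at least one post-baseline MRI, in line with Protocol 10.3.4. Keep the endpoint change table as a description of resolution. Name the reference scan in the Delayed-Start summary too, because under SAP 6.1.2 ARIA that arose in the first 78 weeks would otherwise become part of baseline.

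The cost is SAP wording and a small derivation from central MRI reads already planned, with no new scans. The drawback is that symptom-driven scans are not made equally in all patients. Flag findings that come only from unscheduled scans, so that the reader can see how far they drive any difference between arms.
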